12.3.2 Safety Set

The Safety set will include all randomized subjects who received at least one dose of study treatment (cobomarsen or vorinostat).

12.3.3 Per Protocol Set (PPS)

The PPS will consist of all subjects randomized to the study, who received study treatment, and completed assessments necessary for the evaluation of the primary endpoint with no major protocol deviations that would affect endpoint analysis.

12.3.4 Pharmacokinetic Analysis Set (PKAS)

The PKAS will consist of subjects randomized to cobomarsen who received at least one dose of cobomarsen and had at least one post baseline PK sample taken and analyzed.

12.4 Statistical Methods and Sample Size Justification

12.4.1 General Approach

All statistical analyses will be performed using SAS statistical software, unless otherwise noted. For categorical variables, the number and percent of each category within a parameter will be presented. For continuous variables, the sample size (n), mean, median, standard deviation, minimum and maximum values will be presented. Missing data will not be imputed unless otherwise stated.

12.4.2 Analysis of Demographics and Other Baseline Characteristics

Demographics and other baseline disease characteristics will be summarized by treatment group.

12.4.3 Analysis of the Primary Efficacy Endpoint

The analysis of the primary efficacy endpoint is the proportion of subjects in the randomized period achieving an ORR4 in skin using mSWAT assessments. ORR4 is the proportion of subjects with a CR or PR for 4 consecutive months confirmed by repeat assessments no less than 28 days (\pm 3 days) later ([Olsen et al. 2011](#)).

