The analysis of the primary efficacy endpoint is the proportion of subjects in the randomized period achieving an ORR4 in skin by mSWAT assessments. The statistical test for the primary efficacy endpoint will be one-sided and will be split between the interim and final analysis and conducted using a total 0.025 significance level. Additional details of the primary efficacy endpoint in addition to the secondary efficacy endpoints will be detailed in the statistical analysis plan.

	
Safety analyses will include AEs, concomitant medications, laboratory data, physical examination, and ECG data.
 
The following analysis populations will be defined:
 
Intent to Treat Analysis Set (ITT)
 
The ITT will include all randomized subjects who received at least one dose of study treatment (cobomarsen or vorinostat) and had at least one post-baseline assessment.
 
Safety Set
 
The Safety set will include all randomized subjects who received at least one dose of study treatment (cobomarsen or vorinostat).
 
Per Protocol Set (PPS)
 
The PPS will consist of all subjects randomized to the study, who received study treatment, and completed assessments necessary for the evaluation of the primary endpoint with no major protocol deviations that would affect endpoint analysis.
 
Pharmacokinetic Analysis Set (PKAS)
 
The PKAS will consist of subjects randomized to cobomarsen who received at least one dose of cobomarsen and had at least one post baseline PK sample taken and analyzed.

Sample Size Justification:
	
Total enrollment of approximately 126 subjects randomized 1:1 provides greater than 80% power to detect a 25% difference (35% vs 10%) in the primary outcome, ORR₄, between the investigational product and active comparator groups.

Planned Interim Analysis:
	
An interim analysis will be performed after approximately 40 subjects are followed for a minimum of approximately 6 months.

Trial-specific Committees:
	
Data Monitoring Committee
 
The Data Monitoring Committee (DMC) will be responsible for reviewing safety data at regular intervals as well as to perform the interim analysis for futility. A separate DMC Charter will be established that outlines DMC membership, precisely what data will be reviewed, along with the timing and frequency of the reviews. DMC recommendation will be provided to the Sponsor in compliance with the DMC Charter.

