4.1 Randomized Period

Approximately 126 subjects are expected to be enrolled. An interim analysis will be conducted after approximately 40 subjects have been followed for a minimum of approximately 6 months; enrollment will be suspended after approximately 40 subjects have been enrolled until the completion of the interim analysis.

Subjects will be randomized in a 1:1 ratio to receive cobomarsen or vorinostat. Subjects will undergo Screening lasting up to 28 days from the time of informed consent, followed by active treatment, and then follow-up for response and disease progression.

Figure 1. SOLAR Study Design Schematic

Subjects will remain on their assigned study treatment until one of the following occurs:

1. Disease progression, defined as either (see [Appendix F](#)):
 - a. Confirmed progression in skin
 - b. Clinical progression in other compartments, documented by assessments (flow cytometry and/or CT scan) completed per investigator discretion
 - c. Partial or complete skin response followed by a confirmed loss of skin response as defined by an increase of mSWAT of greater than the sum of nadir plus 50% baseline score.

Progressions based on mSWAT will be confirmed by repeated measurement 28 days (± 3 days) after the first determination of progression.

If confirmed, the date of progression will be based on the first determination of progression. Subjects will continue the study treatment until disease progression is confirmed.

2. Subject meets one of the other treatment discontinuation criteria (see [Section 5.4.1](#)).

Safety assessments will include monitoring the incidence and severity of AEs and SAEs, physical examination findings, vital signs, ECG monitoring, and clinical laboratory assessments.

Samples will be collected for PK in the cobomarsen group on Days 1, 2, 3, 5, 8, 15, 29, and every 4 weeks from Weeks 9 through 81, every 8 weeks thereafter, and at the follow-up/end of treatment visit.

mSWAT evaluations will be completed on Days 1 and 29, every 4 weeks through Week 81, every 8 weeks thereafter, and at the End of Treatment and Follow-up visits. Every effort will be made to perform a final disease assessment for subjects who withdraw from the study early.

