7.5.1.2 Process to Determine Skin Response and Confirmation

Once the Investigator believes that the mSWAT evaluation has shown an objective response for 4 consecutive months (i.e., a PR or CR as assessed per mSWAT criteria, without loss of response, for 4 consecutive months; see [Table F2 in Appendix F](#)), the Investigator must schedule the subject for a visit within 28 days (± 3 days) to perform a confirmatory mSWAT.

Subjects who have a PR or CR cannot be downgraded to stable disease. Subjects who have a PR or CR can only have their response downgraded if they meet the criteria of loss of response (progression) see [Table F2 in Appendix F](#).

Of note: An unconfirmed progression at any time during the study will not preclude the Investigator from assessing a future response (CR or PR).

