11 TRIAL-SPECIFIC COMMITTEES

11.1 Data Monitoring Committee

The Data Monitoring Committee (DMC) will be responsible for reviewing safety data at regular intervals as well as to perform the interim analysis. A separate DMC Charter will be established that outlines DMC membership, precisely what data will be reviewed, along with the timing and frequency of the reviews. DMC recommendations will be provided to the Sponsor in compliance with the DMC Charter.

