12.4.7 Planned Interim Analyses

An interim analysis will be performed after approximately 40 subjects are followed for a minimum of approximately 6 months to allow assessment for a 4-month duration of response (ORR4) from the date of initial objective response. A decision to stop the study at interim analysis for superiority will be considered if the one-sided test statistic p-value is < 0.01 (Pocock, et al. 1977). The number of skin ORR4 events required to demonstrate superiority at the interim analysis are shown in [Table 6](#).

Table 6: ORR4 Events Required to Demonstrate Superiority in Skin Objective Response for Interim Analysis ($p < 0.01$)

Vorinostat (N = 18)	Cobomarsen (N = 18)
0/18	6/18
1/18	8/18
2/18	10/18
3/18	11/18
4/18	12/18
5/18	13/18
6/18	14/18
7/18	15/18
8/18	16/18
9/18	17/18
10/18	18/18
11/18	18/18
12/18	18/18

Enrollment will be halted if data from this study or other cobomarsen studies conclusively demonstrate that cobomarsen does not have significant activity in MF.

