Appendix B. Schedule of Events (On Treatment and Post-Treatment Follow-up – Cobomarsen Group)

Study Procedure or Assessment	On Treatment Visits										Follow-Up and End of Treatment			
	1				2	3	4	5	Weekly Visits from Week 6 through End of Treatment (±3 days)	Q4W Visits from Weeks 9 through 81 then Q8W thereafter (±3 days)	End of Treatment Visit	Follow-up visit: 28 (±5) Days after End of Treatment Visit ^a	Follow-up for Response and Progression ^b	
Study Day	1 ^c	2	3 (+1)	5 (±1)	8 (±1)	15 (±1)	22 (±2)	29 (±3)						
IWRS Transaction (Study Treatment Dispensation)	X		X	X	Weekly starting at Week 2 until End of Treatment Visit						X ^t			
mSWAT ^d	X							X		X	X	X	X ^r	
Vital Signs ^s	X	X	X	X	Weekly starting at Week 2 until End of Treatment Visit						X	X		
Physical Examination ^e	X				X	X		X		X	X	X		
Weight	X							X		X	X	X		
Complement (C5a, Bb) ^f	X	X												
Urine Pregnancy Test	X							X		X ^u	X	X		
Single 12-lead ECG ^g	X							X		X	X	X		
Laboratory Assessments ^h	X		X		X	X		X		X	X	X		
Coagulation ⁱ	X	X			X			X				X		
Sample for PD and ADA (predose)	X					X		X		X	X	X		
Adverse Events ^j	Review on an ongoing basis											X		
Prior and Concomitant Medications ^k	Review on an ongoing basis											X		
Blood PK Sample	X ^l	X ^m	X ⁿ	X ⁿ	X ^o	X ⁿ		X ^l		X ^p	X	X		

Study Procedure or Assessment	On Treatment Visits									Follow-Up and End of Treatment			
	1			2	3	4	5	Weekly Visits from Week 6 through End of Treatment (±3 days)	Q4W Visits from Weeks 9 through 81 then Q8W thereafter (±3 days)	End of Treatment Visit	Follow-up visit: 28 (±5) Days after End of Treatment Visit ^a	Follow-up for Response and Progression ^b	
Study Day	1 ^c	2	3 (+1)	5 (±1)	8 (±1)	15 (±1)	22 (±2)	29 (±3)					
Cobomarsen Infusion ^q	X		X	X	Infusions performed weekly starting at Week 2 until End of Treatment Visit								

Abbreviations: ADA = anti-drug antibodies; AE = adverse event; aPTT = activated partial thromboplastin time; CR = complete response; CT = computed tomography; CTCL = cutaneous T-cell lymphoma; ECG = electrocardiogram; eCRF = electronic case report form; INR = international normalized ratio; IWRS = Interactive Web Response System; MRI = magnetic resonance imaging; mSWAT = Modified Severity Weighted Assessment tool; PD = pharmacodynamic(s); PK = pharmacokinetic(s); PR = partial response; PT = prothrombin time; Q4W = every 4 weeks; Q8W = every 8 weeks; SAE = serious adverse event;; TSH = thyroid-stimulating hormone

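### Sections 7.5.1.2 and 12.4.3 time the confirmation of ORR4 differently, and the synopsis labels as futility an interim that the rest of the plan sets up as a superiority look

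*Combined protocol and SAP*

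**What the plan says.** **Confirmation of ORR4.** Section 12.4.3 (Analysis of the Primary Efficacy Endpoint) reads: "ORR4 is the proportion of subjects with a CR or PR for 4 consecutive months confirmed by repeat assessments no less than 28 days", followed by a ± 3-day tolerance. Section 7.5.1.2 says that once the investigator believes a response has lasted 4 consecutive months, "the Investigator must schedule the subject for a visit within 28 days (± 3 days) to perform a confirmatory mSWAT". On the routine schedule, section 4.1 states: "mSWAT evaluations will be completed on Days 1 and 29, every 4 weeks through Week 81", and every 8 weeks after that. The schedules of events in Appendices B and C give each of these visits its own ± 3-day window.

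**Purpose of the interim.** In the synopsis (Trial-specific Committees) the DMC is to review safety data "as well as to perform the interim analysis for futility". The synopsis (Statistical Methods) also says that the primary test "will be split between the interim and final analysis and conducted using a total 0.025 significance level". Section 11.1 gives the DMC's role without a purpose: "as well as to perform the interim analysis. A separate DMC Charter will be established". Section 12.4.7 states: "A decision to stop the study at interim analysis for superiority will be considered" if the one-sided p-value is below 0.01, and Table 6 lists the counts needed. The same section ends with a provision to halt enrollment if this study or other cobomarsen studies conclusively show a lack of activity. It gives no numeric criterion and does not say whether the provision is part of the interim. Section 12.5.1 charges 1% one-sided alpha to the interim and leaves 1.5% for the final test.

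**The concern.** ORR4 is the primary endpoint, and two sections bound its confirmation from opposite sides. One sets a latest date and the other an earliest date. A site can follow its instruction exactly, see the subject on Day 20, and produce a visit that the analysis section does not accept as confirmation. The trial is open-label and mSWAT is scored at the site, so it should be clear before any data are examined which visits confirm a response.

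On the interim, a reader of the synopsis would expect a futility look. A reader of 12.4.7 would expect a superiority look with a separate, non-numeric inactivity halt. Section 4.1 suspends enrollment until this analysis is complete, so the protocol should say in one voice what the analysis is for.

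**Working it through.** **1. The two confirmation rules side by side** (days after the 4-month assessment)

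| Day of the confirmatory mSWAT | 7.5.1.2: no later than 28 + 3 = Day 31 | 12.4.3: no earlier than 28 − 3 = Day 25 |
|---|---|---|
| Before Day 25 | on schedule | does not confirm |
| Days 25–31 | on schedule | confirms |
| After Day 31 | off schedule | confirms |

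**2. Can routine visits fall outside Days 25–31?** Assumption: the confirmatory mSWAT is the next 4-weekly visit. Let the two visits be a and b days off nominal, each from −3 to +3. The gap is 28 + b − a, so it runs from 22 to 34 days.
- Visit days spread evenly over the window: P(gap < 25) = 6/49 = 12.2%.
- Visit days clustered on the nominal day (weights 1-2-3-4-3-2-1): P(gap < 25) = 15/256 = 5.9%.
- The shares above Day 31 are the same by symmetry, but those visits confirm under 12.4.3.
- Visits timed 25–31 days from the actual 4-month assessment: 0%.

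**3. The plan's own power.** Inputs from 12.5.1: n = 63 per arm, 35% v 10%, one-sided alpha 0.015, pooled normal approximation with continuity correction.
- Power = Φ{[d − 1/n − z·SE0]/SE1}
- d = 0.25; 1/n = 0.0159; z = 2.170
- Pooled rate 0.225, so SE0 = √(2 × 0.225 × 0.775/63) = 0.0744
- SE1 = √[(0.35 × 0.65 + 0.10 × 0.90)/63] = 0.0710
- Power = Φ(1.024) = 84.7%, which agrees with the stated figure of more than 80%.

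**4. Power with the conflict left in place.** Under 12.4.3 a visit before Day 25 does not confirm, but a later mSWAT with continuing response does. A responder is lost only if response ends or the subject drops out before that later mSWAT. The documents give no rate for this; 5% to 30% is assumed, equal in both arms. Both response rates are multiplied by 1 − (early share × loss share).

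| Early share | Loss share | Rates | Power |
|---|---|---|---|
| 12.2% | 5% | 34.8% v 9.9% | 84.3% |
| 12.2% | 30% | 33.7% v 9.6% | 82.5% |
| 5.9% | 5% | 34.9% v 10.0% | 84.5% |
| 5.9% | 30% | 34.4% v 9.8% | 83.7% |

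**5. The interim statements compared**

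| Place | Purpose given |
|---|---|
| Synopsis, Trial-specific Committees | futility |
| Synopsis, Statistical Methods | alpha split between interim and final, so an efficacy test |
| 11.1 | none |
| 12.4.7 and Table 6 | superiority, one-sided p < 0.01 |
| 12.4.7, last sentence | inactivity halt, no number, link to the interim not stated |
| 12.5.1 | interim alpha 1%, final 1.5% |

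The alpha adds up: 0.01 + 0.015 = 0.025. Every row of Table 6 meets one-sided Fisher p < 0.01 at 18 per arm. For example, 6 v 0 gives p = 0.0095 and 5 v 0 gives p = 0.0227. No futility boundary appears anywhere, so no futility probability can be computed.

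**The case against.** The best case against the first part is that only 12.4.3 defines the endpoint. Section 7.5.1.2 is a scheduling instruction, its ± 3 days suggests a 28-day target visit, and progression is confirmed at the same 28 (± 3) days. On that reading a visit after Day 31 is only a timing deviation and costs no responder. This stands for late visits. It does not settle early ones, because read as written 7.5.1.2 sets no earliest day.

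A reader might infer that rejecting every early visit takes power to about 81% (clustered visits) or 77% (evenly spread visits). The documents do not support this. It requires that no later mSWAT may confirm, whereas 12.4.3 has no upper limit, mSWAT continues on or off treatment (7.5.1), and a response can be downgraded only by loss of response (7.5.1.2). The 8-weekly schedule after Week 81 might also look like a gap. It concerns only 4-month points reached at Week 81 or later, and 7.5.1.2 already requires the extra visit.

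On the second part, it can be said that the futility wording is one stray phrase, outweighed by everything else, and that the DMC charter and the SAP hold the detail. This is largely right about consequence. A separate charter still does not remove a contradiction inside the protocol.

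A reader might also infer that a 6-month minimum is too short for confirmed responses, and attach a loss in the chance of crossing Table 6. That needs a distribution of response onset and an accrual pattern that the documents do not give, and 6 months is an approximate floor. No magnitude is claimed here. Nor does either contradiction require a rule on how the DMC should regard responses not yet confirmed.

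**Conclusion.** Both inconsistencies are real, and no section of the protocol reconciles them. The first matters more, because it touches the definition of the primary endpoint: a visit before Day 25 satisfies 7.5.1.2 and does not confirm under 12.4.3. Its expected size is small. Power is about 82.5 to 84.5% against 84.7%, assuming that confirmation falls at the next 4-weekly visit, that visit days are spread evenly or clustered within ± 3 days, and that 5 to 30% of responders with a too-early visit are lost before a later mSWAT. The stated power of more than 80% holds throughout. The second is a matter of labelling: the plan's operative content is a superiority look at one-sided p < 0.01, with an inactivity halt whose link to the interim is not stated. It has no effect on alpha, sample size or power. The changes should be made because they are cheap and concern the primary endpoint, not because the design fails.

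**What to change.** 1. In 7.5.1.2, schedule the confirmatory mSWAT 28 days (± 3), and not before Day 25, counted from the actual date of the 4-month assessment.
2. In 12.4.3, state that a later mSWAT with continuing response also confirms. This sentence is needed: a closed 28 (± 3)-day window alone would exclude later confirmations that 12.4.3 now counts.
3. In the synopsis, replace the futility wording so that the synopsis, 11.1 and 12.4.7 give the same purpose: superiority at one-sided p < 0.01.
4. In 12.4.7, say whether the inactivity halt is part of this interim.

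The cost is wording only. Sample size, alpha and stated power are unchanged. Through Week 81 no visit is added, because a gap of exactly 28 days from the actual assessment always falls inside the next visit's ± 3-day window (b = a gives 28). After Week 81 the confirmatory visit is already required by 7.5.1.2.

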12.4.4 Analysis of the Secondary Endpoints

The secondary endpoint of progression-free survival is defined as the time from randomization to the date of the earliest documented progression or death due to any cause.

Time to event analyses (Kaplan-Meier) will be done for PFS, time to \geq 50% mSWAT improvement, time to maximal effect in skin, duration of maintaining response in skin, CRR, and TTP. For responding subjects, duration of response and duration of \geq 50% improvement will be displayed.

Summary statistics for change from Baseline for mSWAT scores will be presented by treatment and visit.

The percent of subjects achieving $\geq 50\%$ improvement in mSWAT scores will be presented by treatment for:

- $\geq 50\%$ improvement for at least 28 days;
- $\geq 50\%$ improvement at 4 months;
- $\geq 50\%$ improvement at 28 days.

The N (%) of complete responses will be presented by treatment.

P-values generated from secondary analyses are supportive only. The mean change from baseline in use of pruritus medication will be presented by treatment and visit.

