3.2.2 Secondary Endpoints

Efficacy measures:

- Progression-free survival (PFS).
- Complete response rate (CRR).
- Time to progression (TTP).
- Time to maximal effect in skin (mSWAT).
- Proportion of subjects achieving $\geq 50\%$ improvement in mSWAT of at least 28-days duration (ORR1).
- Proportion of subjects achieving $\geq 50\%$ improvement in mSWAT from baseline at 28 days and at 4 months.
- Time to $\geq 50\%$ improvement in mSWAT.
- Duration of response in skin (no progression after achieving $\geq 50\%$ improvement in mSWAT).
- Change in pruritus medication utilization from baseline and incidence of pruritus medication utilization.

- During the crossover portion of the study:
 - Proportion of subjects achieving an objective skin response (complete response [CR] or partial response [PR]) of at least 4 months duration (ORR4) using the mSWAT scoring (see [Appendix F](#)).
 - Progression-free survival (PFS).
 - Complete response rate (CRR)
 - Time to progression (TTP).
 - Time to maximal effect in skin (mSWAT).
 - Proportion of subjects achieving $\geq 50\%$ improvement in mSWAT of at least 28-days duration (ORR1).
 - Proportion of subjects achieving $\geq 50\%$ improvement in mSWAT from baseline at 28 days and at 4 months.
 - Time to $\geq 50\%$ improvement in mSWAT.
 - Duration of response in skin (no progression after achieving $\geq 50\%$ improvement in mSWAT).
 - Change in pruritus medication utilization from baseline and incidence of pruritus medication utilization.

Safety and Tolerability Evaluations:

- Incidence and severity of clinically significant AEs (including grade 3 and 4 AEs, treatment-related AEs, SAEs, and AEs requiring discontinuation), physical examination findings, changes in electrocardiogram (ECGs), changes in laboratory parameters and changes in vital signs.
- Characterization of anti-drug antibody generation.

Pharmacokinetic Evaluation:

- Population PK parameters.
- During the crossover portion of the study
 - Pharmacokinetic C_{\max} and trough concentration analysis

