7.5 Efficacy Assessments

7.5.1 Response and Disease Progression Evaluations and mSWAT

Response to study treatment and disease progression will be evaluated using skin response criteria for MF (Olsen et al. 2011; see [Appendix F](#)).

mSWAT evaluations should be performed per the visit schedule (see [Appendix B](#), [Appendix C](#), [Appendix D](#) and [Appendix E](#)) whether the subject is receiving study treatment or has discontinued treatment, until one of the following (whichever occurs first): disease progression in skin (confirmed by repeat measurement 28 days [\pm 3 days] after the first determination of progression), lymph nodes, blood or viscera, withdrawal of consent, initiation of subsequent MF treatment, lost to follow-up, or death.

mSWAT evaluations may also be performed at any time the Investigator suspects there is clinical evidence of disease progression.

In the event the investigator declares disease progression in other compartments, based on assessments (flow cytometry or CT scan) performed at his/her own discretion, documentation of progression by standard Olsen criteria ([Appendix F](#)) should be provided.

7.5.1.1 mSWAT Evaluations (Skin Component)

mSWAT (see [Appendix F](#)) scoring will be performed at Screening and before dosing at the time points outlined in [Appendix B](#), [Appendix C](#) and [Appendix E](#).

Every effort should be made to have the same mSWAT evaluator conduct all assessments of mSWAT for a subject at Screening and throughout the study to ensure consistency.

If the primary evaluator is not available during the visit window, the following should occur, in order of preference:

- 1. The visit could be postponed or performed earlier by the primary evaluator.**
- 2. The visit could be performed by another locally trained evaluator. If a different evaluator conducts an mSWAT a review of the previous mSWAT should occur prior to the evaluation of the current mSWAT. If the new assessment impacts a response or progression there should be clear documentation (e.g. photography) to support the results.**

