7.5.1.3 Process to Determine Disease Progression

As stated in [Section 4](#), disease progression is defined as either:

- a. Confirmed progression in skin
- b. Clinical progression in in other compartments, documented by assessments (flow cytometry and/or CT scan) completed per investigator discretion
- c. Partial or complete skin response followed by a confirmed loss of skin response as defined by an increase of mSWAT of greater than the sum of nadir plus 50% baseline score.

Progressions based on mSWAT will be confirmed by repeat measurement 28 days (± 3 days) after the first determination of progression. If the subject is currently on study treatment, the study treatment should not be discontinued until confirmation of disease progression.

An unconfirmed progression would not preclude future responses (CR or PR).

Upon reassessment, if the original findings have not changed, and there is no alternate clinical explanation or etiology for the suspected progression, then disease progression should be considered confirmed and the date of disease progression should be reported as the date that it was first suspected.

Subjects who meet disease progression criteria in skin, or other compartment assessed per investigator discretion, should be discontinued from study treatment due to disease progression.

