12.5.2 Key Secondary Endpoint Sample Size

The null hypothesis is that there is no difference in progression free survival (PFS) between cobomarsen and vorinostat. A sample size of 126 subjects (63 per group; 66 events) provides at least 80% power to detect a difference between vorinostat and cobomarsen, assuming a median PFS of 4 months for vorinostat and 8 months for cobomarsen. This calculation is based on a one-sided, logrank test at the 0.025 level of significance, assuming 15 months of recruitment, 6 months of follow-up, and 17% censoring. No interim analysis is planned for PFS.

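### Kaplan-Meier is the only method named for time to at least 50% mSWAT improvement, with no rule for progression, death or new MF therapy before response; default censoring would overstate the chance of response

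*Combined protocol and SAP*

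**What the plan says.** Section 12.4.4 of the protocol reads "Time to event analyses (Kaplan-Meier) will be done for PFS, time to" at least 50% mSWAT improvement and time to maximal effect in skin, and continues with "duration of maintaining response in skin, CRR, and TTP". Kaplan-Meier is the only method named for this list. There is no censoring rule, no competing-event method and no between-arm test for the response-time endpoints. The same section also plans a count and percentage of complete responses by arm, and percentages with at least 50% improvement (sustained for at least 28 days, at 28 days and at 4 months). It adds: "P-values generated from secondary analyses are supportive only".

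Section 7.5.1 has mSWAT performed "until one of the following (whichever occurs first): disease progression in skin" (confirmed), progression in another compartment, withdrawal of consent, new MF treatment, loss to follow-up or death. Sections 5.4.1 and 8.5 end follow-up for progression in essentially the same way. Section 7.5.1.3 qualifies this: "An unconfirmed progression would not preclude future responses (CR or PR"). Only confirmed skin progression, or progression elsewhere, therefore closes observation. Under section 4.2, vorinostat subjects with confirmed skin progression may then cross over to cobomarsen, where response is a separate endpoint.

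Section 3.2.2 lists "Time to maximal effect in skin (mSWAT") without saying what the event is. Section 12.1 and the synopsis leave detailed methods to an SAP to be completed before database lock. The file contains no separate SAP text.

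**The concern.** A subject who progresses without having reached 50% improvement comes off study treatment and is no longer scored in that period. Response on the assigned arm can no longer be observed for that subject, so progression is a competing event for response. If the subject is censored there, Kaplan-Meier treats them as still able to respond, at the same rate as those who remain under observation. The curve then estimates response in a hypothetical setting where nobody progresses, and 1-KM exceeds the proportion who actually respond.

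The excess grows with the progression rate, and the plan expects that rate to differ by arm, so the two curves would be inflated unequally. At stake are the reported response curves, any medians read from them, and the descriptive comparison of arms. The curves could also sit well above the responder percentages that the same section asks for. CRR raises a separate problem: a rate has no event time, so its place in the list has no clear meaning unless time to CR is intended.

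**Working it through.** **Inputs.** Allocation: "Subjects will be randomized in a 1:1 ratio to receive cobomarsen or vorinostat" (section 4.1). Median PFS 4 months on vorinostat and 8 on cobomarsen (section 12.5.2). Response rates for illustration: 35% and 10%, the ORR4 planning rates (section 12.5.1); 63%, which is 5 of 8 Phase 1 subjects on cobomarsen (section 2.1.3.2); and 31%, the vorinostat figure from earlier trials (section 2.2). The documents give no figures for time to response.

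**The plan's own figure.** Section 12.5.2: "A sample size of 126 subjects (63 per group; 66 events) provides at least 80% power". With exponential PFS the hazard ratio is 4/8 = 0.5. The Schoenfeld formula at one-sided 0.025 and 80% power gives 4 × (1.960 + 0.842)² / (ln 0.5)² = 65.3, so 66 events; power at 66 events is 80.4%. The figure reproduces, which confirms how the two medians are to be read.

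**Model (assumed).** Response and progression have independent constant hazards, and the PFS medians stand in for progression before response.

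- Progression hazard: hp = ln 2 / median, i.e. 0.1733 per month on vorinostat and 0.0866 on cobomarsen.
- Response hazard giving eventual response proportion F: hr = hp × F / (1 − F).
- True cumulative incidence: CI(t) = F × [1 − exp(−(hr + hp)t)].
- Kaplan-Meier with progressors censored: 1-KM(t) = 1 − exp(−hr × t).

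**Results at t = 12 months.**

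| Arm, eventual rate F | hr | True CI | 1-KM | Excess (points) |
|---|---|---|---|---|
| Vorinostat, 10% | 0.0193 | 9.0% | 20.6% | 11.6 |
| Cobomarsen, 35% | 0.0467 | 27.9% | 42.9% | 14.9 |
| Vorinostat, 31% | 0.0779 | 29.5% | 60.7% | 31.2 |
| Cobomarsen, 63% | 0.1475 | 59.2% | 83.0% | 23.8 |

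**Arm difference (cobomarsen minus vorinostat).**

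- 35% v 10%: true 27.9 − 9.0 = 18.9 points; 1-KM 42.9 − 20.6 = 22.2 (from unrounded values). The difference grows.
- 63% v 31%: true 59.2 − 29.5 = 29.7 points; 1-KM 83.0 − 60.7 = 22.3. The difference shrinks.

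**Equal true response.** If hr is instead solved so that true 12-month incidence is 31% in both arms, 1-KM reads 47% on cobomarsen and 63% on vorinostat. That is an apparent 16-point deficit for cobomarsen where there is none.

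**Alternative handling.** If non-responders who progress stay in the risk set to a common cut-off, and nothing else is censored before it, 1-KM equals the cumulative incidence and the excess is zero.

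**The case against.** The strongest reply is that no passage says progression is to be censored. A reader might infer that the plan prescribes this. It does not: section 12.4.4 is silent, and an SAP still to be written could keep progressors at risk. That is right as far as it goes. But Kaplan-Meier is the only method named, observation stops at progression, and nothing in the file keeps those subjects at risk, so run as written the default is to censor them.

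A reader might also infer that the arm comparison is distorted in a known direction. The documents do not support that. The sign depends on the response rates assumed, and none of those used is a planning value for this endpoint: ORR4 is stricter than reaching 50% improvement; the 31% is a one-month rate from a population that included Sézary syndrome and large cell transformation, whereas Sézary syndrome and current transformation are excluded here; the 63% rests on 8 subjects. No between-arm test is specified either, and a logrank test that censors progressors would still validly compare cause-specific hazards.

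It is tempting to extend the point to time to maximal effect. If the event is the time of each subject's best score, everyone with post-baseline data has an event and progression need not compete. The gap there is the definition.

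Finally, response is also reported directly as percentages, complete response as N (%), and the endpoints lie outside the ORR4-then-PFS step-down of section 12.2. All of this stands and limits the consequences. It does not make the curves correct.

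**Conclusion.** The point holds for time to at least 50% mSWAT improvement, and for time to CR if that is what listing CRR means. Under default censoring, 1-KM overstates the probability of response in both arms, by unequal amounts. The 12-month excess of about 12 to 31 points is an illustration. It rests on independent constant hazards, on PFS medians (which also count deaths and progression after response) as a proxy for progression before response, and on borrowed response rates. That there is an upward bias in each arm does not depend on those particular values; its size, and its effect on the absolute arm difference, do.

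This is a minor point about the reporting of secondary endpoints. It would be too strong to say that the efficacy conclusions are at risk: sample size, alpha, power and the primary and PFS tests are untouched.

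**What to change.** In section 12.4.4 and the SAP:

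1. For time to at least 50% improvement, replace Kaplan-Meier with Aalen-Johansen cumulative incidence by arm. Progression, death and new MF therapy (including crossover) before response are the competing events. Keeping such non-responders at risk to a common cut-off gives the same answer when there is no other censoring before that cut-off.
2. State that an unconfirmed progression is not a competing event, in line with section 7.5.1.3.
3. Remove CRR from the Kaplan-Meier list, since the N (%) summary is already planned. If time to CR is wanted, name it and treat it as in item 1.
4. Define the event for time to maximal effect first, then choose its method. Label any responders-only summary as descriptive, because it selects subjects on a post-randomization outcome.
5. Keep Kaplan-Meier for PFS, where progression and death are the event.

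The cost is a few sentences of SAP text and a small amount of extra analysis in standard software. The response curves will look less favourable than 1-KM curves. No design parameter changes.
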